2.2 The secondary objectives

The secondary objectives of this study are as follows:

- To assess the efficacy of D20 for prevention of development of gastric and/or duodenal ulcer in patients with a history of gastric and/or duodenal ulcer receiving daily NSAID therapy by evaluating the following:
 - Presence/absence of gastric and/or duodenal ulcers at Weeks 4,12, 24 and 52 after initial administration
 - Severity of gastric mucosal lesion evaluated by modified LANZA score ([Lanza FL, et al., 1988](#)) at Weeks 4, 12, 24 and 52 after initial administration
 - Presence/absence and severity of NSAID-associated gastrointestinal (GI) symptoms assessed by investigator(s) every 4 weeks from Week 4 to Week 52 after initial administration

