3. STUDY PLAN AND PROCEDURES

3.1 Overall study design and flow chart

This Clinical Study Protocol has been subjected to a peer review according to AstraZeneca standard procedures.

This study is designed as a multicentre, open-label, single arm, long-term study involving patients with a history of gastric and/or duodenal ulcers receiving daily NSAID therapy.

A total of 130 patients with a history of gastric and/or duodenal ulcers with ulcer scar confirmed by the esophagogastroduodenoscopy (EGD) performed at screening will receive D20.

The safety of the concomitant use of D961H and NSAID for a long-term period will be assessed. The efficacy of D20 will be also assessed after 52-week oral administration based on the results of the EGD performed at Weeks 4, 12, 24 and 52 after initial administration to verify presence or absence of gastric and/or duodenal ulcers, and to evaluate the severity of gastric and/or duodenal mucosal lesion at Weeks 4, 12, 24 and 52 after initial administration according to modified LANZA score, and investigator's assessment for presence/absence and severity of GI symptoms performed every 4 weeks. If development of gastric and/or duodenal ulcer is observed, the patient will be discontinued from the study.

Findings of EGD including those judged from screening results with an evidence of an ulcer scar and those judged by the investigator(s) after initial administration as gastric and/or duodenal ulcers will be reviewed as needed by the central evaluation committee (see Section 6.7) established by AstraZeneca K.K..

An interim analysis will be performed when 24-week data is locked. The results from this analysis will be submitted to the authority for application for drug approval.

[Table 2](#) shows the study plan including frequency and time of visits.

Table 2 Study Plan

Period	Screening		Study Treatment								
	1	Regis- tration 2	3	4	5	6 7	8	9 10	11	12 13 14	15 or at disc onti nuat ion ^k
Number of weeks before and after Visit 2	2W – 0	0	4W	8W	12W	16W 20W	24W	28W 32W	36W	40W 44W 48W	52W -
Time window	-	-	±4d	±4d	±4d	±4d	±4d	±7d	±7d	±7d	±7d
Informed consent ^a	X										
Inclusion/exclusion criteria	X	X									
Demographic data	X										
Medical/surgical history	X										
Complications	X	X									
Physical examination	X	X	X	X	X	X	X	X	X	X	X
Vital signs	X		X	X	X	X	X	X	X	X	X
Clinical laboratory tests ^{b, c}	X		X	X ^l	X	X ^l	X	X ^l	X	X ^l	X
Pregnancy test (urine) ^d	X										
Hp test (IgG antibody)	X ^m										

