Pepsinogen I/II	X										
Genetic test for CYP2C19	X ^m										
EGD ^e											
- Confirmation of presence/absence of gastric and/or duodenal ulcer ^e	X ⁿ		X		X		X				X
- Assessment of severity of gastric mucosal lesions ^f	X ⁿ		X		X		X				X
- Assessment of gastric mucosal atrophy expansion ^g	X ⁿ										
Evaluation of NSAID-associated GI symptoms by the investigator ^h		X	X	X	X	X	X	X	X	X	X
Registration		X									

Table 2 Study Plan

Period	Screening		Study Treatment								
	1	Regis- tration 2	3	4	5	6 7	8	9 10	11	12 13 14	15 or at disc onti nuat ion ^k
Number of weeks before and after Visit 2	2W – 0	0	4W	8W	12W	16W 20W	24W	28W 32W	36W	40W 44W 48W	52W -
Time window	-	-	±4d	±4d	±4d	±4d	±4d	±7d	±7d	±7d	±7d
Dispense the investigational products		X	X	X	X	X	X	X	X	X	
Confirm/collect the remaining investigational products			X	X	X	X	X	X	X	X	X
Compliance status of D961H and NSAID ^l			X	X	X	X	X	X	X	X	X
AE confirmation ^l	←										→
Concomitant therapy/drug	←										→

- a Should be obtained within 4 weeks prior to Visit 2 (registration)
- b Clinical laboratory tests will be conducted at the central laboratory. The investigator(s) may confirm the eligibility of the subjects based on the results of measurements taken at the local laboratory within two weeks prior to registration, even if the measurement values were obtained before informed consent was given. However, baseline clinical laboratory values should be measured at the central laboratory within two weeks prior to registration.
- c The subject must fast (for clinical laboratory tests, the subject must fast only for biochemistry tests).
- d Pregnancy test will be conducted for premenopausal women of childbearing potential.
- e According to the Sakita/Miwa classification.
- f According to the modified LANZA score.
- g According to the Kimura/Takemoto classification.
- h The subject will complete the medical interview form (see Appendix D) at visit and the investigator(s) will confirm the contents of the form to assess severity of each symptom based on the severity classification.
- i The subject will be instructed to record compliance of taking NSAID daily in Patient’s Diary (see Appendix E) and bring the Diary at each visit for confirmation of the compliance.

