3.3.5 Discontinuation of subjects from study treatment or assessment

3.3.5.1 Criteria for discontinuation

Subjects may be discontinued from study treatment and assessments at any time.

Specific reasons for discontinuing a subject from this study are:

- Voluntary discontinuation by the subject who is at any time free to discontinue his/her participation in the study, without prejudice to further treatment
- Safety reasons as judged as the patient to be discontinued by the investigator(s) and/or AstraZeneca K.K.
- Severe non-compliance to protocol as judged by the investigator(s) and/or AstraZeneca K.K.
- Incorrect enrolment i.e., the subject does not meet the required inclusion/exclusion criteria for the study
- Subject lost to follow-up
- Occurrence of an event in conflict of exclusion criteria (e.g., pregnancy)
- Development of gastric and/or duodenal ulcer
- Difficulty to conduct the study as judged by the investigator(s) due to the presence of gastric and/or duodenal mucosal lesion such as bleeding.
- Permanently stopping treatment with daily NSAID
- Others as judged appropriate by the investigator(s) (reasons for discontinuation must be recorded in eCRF)

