4.6.2 Severity of gastric mucosal lesions

4.6.2.1 Methods of assessment

At Visits 1, 3, 5, 8 and 15 (at screening, Weeks 4, 12, 24 and 52 after initial administration), EGD will be performed to evaluate the severity of gastric mucosal lesions (erosion, haemorrhage) by modified LANZA score.

Modified LANZA Score:

- 0: Absence of haemorrhage and erosion
- +1: One haemorrhage or erosion
- +2: 2-10 haemorrhage or erosion
- +3: 11-25 haemorrhages or erosion
- +4: > 25 haemorrhage or erosion or an ulcer

4.6.3 Presence/absence and severity of NSAID-associated GI symptoms (assessment by investigator(s))

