4.7.1.2 Recording of AEs

For AEs spontaneously reported by the subject and/or in response to an open question “Have you had any health problems since the previous visit/during the study period?” asked by the investigator(s) or revealed by observation, only those occurring from initial administration to the last scheduled visit or withdrawal will be recorded at each visit.

For SAEs and AEs resulted in the subject’s withdrawal, those occurred from the time when informed consent was obtained throughout the last scheduled visit or until withdrawal will be recorded at each visit.

In case any AE occurs, details (such as a description of the event, seriousness, maximum intensity, date of onset, date of resolution, outcome, action taken [investigational products], and causality with the investigational products) should be recorded in the eCRF.

(a) Abnormal findings

The investigator(s) will confirm whether clinically important values and changes from baseline on clinical laboratory or vital signs are observed or not. If any, such findings will be recorded in the specified module of eCRFs. However, if the abnormality meets any of the following criteria, the abnormality should be recorded in eCRF as AE:

- The abnormality results in discontinuation of the study.
- The abnormality meets any criterion for SAE.
- Investigator(s) insists it should be reported as an AE.

If the abnormality is associated with clinical signs and symptoms, the sign/symptom should be recorded in eCRF as AE.

If any abnormal laboratory values and vital signs considered as clinically important values or changes were observed at the time of completion or discontinuation of the study treatment, the investigator(s) will perform additional tests and follow-up until they are recovered or until the investigator(s) consider it is not necessary to be followed. However, there is no need to record the test results in the eCRF. The monitor will record the follow-up results on the monitoring visit report.

(b) Symptoms (gastric and/or duodenal ulcers) under study

Occurrence or deterioration of EGD findings (ulcer, erosion, bleeding) will not be recorded in the eCRF as AEs since they will be included in the efficacy evaluation, unless the symptom or finding is serious according to the definitions (See Section 4.7.1.1) or leading to withdrawal from the study due to reasons other than ulcer.

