6.2.2 Secondary variables

The secondary variables of this study are as follows:

Efficacy variables

- Presence or absence of gastric and/or duodenal ulcers at Weeks 4, 12, 24 and 52 after initial administration
- Severity of gastric mucosal lesion by modified LANZA score at Weeks 4, 12, 24 and 52 after initial administration
- Presence/absence and severity of NSAID-associated GI symptoms assessed by the investigator(s) every 4 weeks from Week 4 to Week 52 after initial administration

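### The AE exemption for endoscopic erosion and bleeding rests on a reason that fails for duodenal lesions short of an ulcer, because the modified LANZA score is gastric only everywhere except one sentence of Section 3.1

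*Protocol*

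**What the plan says.** Section 3.1 describes the endoscopies at Weeks 4, 12, 24 and 52 and says the modified LANZA score serves "to evaluate the severity of gastric and/or duodenal mucosal lesion at Weeks 4, 12, 24 and 52 after initial administration". Table 2, in the same section, names the procedure differently: "Assessment of severity of gastric mucosal lesions".

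The secondary objective in Section 2.2 reads "Severity of gastric mucosal lesion evaluated by modified LANZA score". Section 4.6.2.1 says "EGD will be performed to evaluate the severity of gastric mucosal lesions (erosion, haemorrhage) by modified LANZA score", and Section 6.2.2 lists "Severity of gastric mucosal lesion by modified LANZA score at Weeks 4, 12, 24 and 52 after initial administration". The synopsis, Table 4 and Section 6.4.2.2 also refer to the stomach only.

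The one other endoscopic efficacy variable, in Section 4.6.1.1, is presence or absence of gastric and/or duodenal ulcer. It counts an ulcer only in Sakita/Miwa stages A1, A2, H1 or H2.

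Section 4.7.1.2(b) deals with endoscopic ulcer, erosion and bleeding that appear or get worse. These "will not be recorded in the eCRF as AEs since they will be included in the efficacy evaluation". There are two exceptions: the finding is serious, or it takes the subject out of the study on a ground other than ulcer. The rule names no anatomical site for erosion or bleeding.

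**The concern.** The exemption gives one reason: the findings are already counted as efficacy. That is sound only for findings that an efficacy variable does count. The ulcer variable covers stomach and duodenum, but erosions and bleeding reach the efficacy data only through the LANZA score. If that score is gastric, a duodenal erosion or bleed without an ulcer is excused from AE recording on a ground that is not true of it.

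AEs are a primary variable of this study, and the duodenum is within its scope. A duodenal scar qualifies a subject for entry, and the ulcer site list includes the bulb and the retrobulbar region. What centres enter as an AE is fixed by the protocol, so a finding that was never recorded cannot be recovered at analysis.

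The contradictory sentence in Section 3.1 adds a second problem. Centres that follow different sections would apply one score to different anatomy.

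**Working it through.** There is no stated figure to reproduce. The check compares each statement of the score's scope with the recording rule.

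**Scope of the modified LANZA score**

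| Place in the protocol | Scope |
|---|---|
| Section 3.1, text | gastric and/or duodenal |
| Synopsis | gastric |
| Section 2.2, objectives | gastric |
| Table 2, study plan | gastric |
| Table 4 | gastric |
| Section 4.6.2, methods | gastric |
| Section 6.2.2, variables | gastric |
| Section 6.4.2.2, analysis | gastric |

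One place says gastric and/or duodenal, and seven say gastric. The grades do not settle it, because they name no site: the lowest is "0: Absence of haemorrhage and erosion". The gastric limit comes only from the surrounding text.

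**Where a new or worse duodenal finding goes if the score is gastric only**

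1. Ulcer in stage A1 to H2: captured by the ulcer variable.
2. Erosion or bleeding without such an ulcer, serious: recorded as an AE under the first exception.
3. The same, non-serious, but the subject leaves the study because of it: recorded as an AE under the second exception. Section 3.3.5.1 makes this a foreseeable route, since it lists difficulty in conducting the study "due to the presence of gastric and/or duodenal mucosal lesion such as bleeding" among the grounds for discontinuation.
4. The same, non-serious, and the subject continues: not in the ulcer variable, not in the LANZA score, and exempt from AE recording.

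Only the fourth path is a gap. Without the exemption, such a finding could be recorded, because the AE definition in Section 4.7.1.1 covers signs and abnormal investigation results.

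**Where it goes if a centre follows Section 3.1**

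The fourth kind of finding is counted in the LANZA score and the gap closes at that centre. About 20 centres are planned. If some count duodenal lesions and others do not, the pooled scores and changes from baseline in Section 6.4.2.2 mix two definitions.

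**The case against.** The strongest reply is that the problem is small and conditional. Much of that is right.

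- The gap depends on which text governs. If Section 3.1 does, nothing is lost. This is true, but the score then varies by centre unless all centres read it that way, and seven places point to gastric only.
- A centre could read the exemption as reaching no further than its own reason, and so record a duodenal erosion under the general AE definition. That reading is possible. However, the rule names erosion and bleeding without a site, under a heading that mentions both gastric and duodenal ulcers, so a centre that omits the finding is also following the text.
- Section 3.3.5.1 might seem to make matters worse by treating duodenal bleeding as grave enough to end participation. It works the other way, because a lesion that ends participation meets the second exception and is recorded.
- A reader might infer that early duodenal damage leaves no trace in any dataset. The protocol does not support this. Six GI symptoms are graded at registration and every 4 weeks. Haematology is taken at screening and at every visit from Week 4 (6 + 8 = 14 samples, as in Table 6). Clinically important laboratory changes have their own eCRF module, and associated signs or symptoms are AEs. The eCRF itself is not at hand.
- A reader might also infer that the objectives go unanswered for the duodenum. They do not. The efficacy objective concerns gastric and duodenal ulcers, and duodenal ulcers are recorded. No objective asks for duodenal mucosal protection short of ulcer.

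What stands after this is a recording rule for a primary variable whose stated reason is untrue for one class of finding, and a score whose scope is stated in two ways.

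**Conclusion.** The point holds in a narrow form. Under the gastric-only definition, duodenal erosions or bleeding short of an A1 to H2 ulcer that are non-serious and do not cause withdrawal enter neither an efficacy variable nor the AE record. If some centres follow Section 3.1 instead, the LANZA score is not comparable across centres.

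The number of lesions affected cannot be estimated from the protocol, which gives no rate for duodenal erosion or bleeding. Two figures are tempting and should not be used as its size:

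- The survey cited in Section 1.1.2 gives 15.5% gastric and 1.9% duodenal ulcer, so 1.9 / (15.5 + 1.9) = 10.9% of the two combined. This is a split of ulcers, which the trial does record, and nothing shows that erosions follow it.
- 130 subjects x 4 on-treatment endoscopies = 520. This is the most examinations that could take place with no dropout, not a count of unrecorded lesions.

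The conclusion assumes that centres apply Section 4.7.1.2(b) as worded and that no eCRF instruction overrides it. The ulcer-free estimates are not affected. The point is worth correcting before recruitment because it concerns what is collected.

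**What to change.** Make two edits to the protocol text.

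1. In Section 3.1, change the scope of the LANZA assessment to gastric mucosal lesions, to match Sections 4.6.2, 6.2.2 and 6.4.2.2.
2. In Section 4.7.1.2(b), limit the exemption to findings that an efficacy variable captures: gastric erosion or haemorrhage, and gastric or duodenal ulcer. Other new or worse endoscopic findings then fall under the general AE rules.

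No endoscopy, reader or analysis is added. The cost is a few more non-serious AE records. A separate duodenal erosion and haemorrhage score would also close the gap, but no objective requires it. It would need a new variable in Sections 4.6.2, 6.2.2 and 6.4.2.2 and a new eCRF field, so it is optional.

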3.2 Rationale and risk/benefit assessment

3.2.1 Rationale for study design, doses and control groups

A risk factor for development of NSAID-associated peptic ulcers

The results of the survey conducted by the Japan Rheumatism Foundation show that the prevalence rate of gastric ulcer accounted for 32.7% in patients with a history of gastric ulcer significantly higher than those without a history of gastric ulcer (11.8%) among the patients receiving daily NSAID. The prevalence rate of duodenal ulcer accounted for 10% in patients with a history of duodenal ulcer significantly higher than those without a history of duodenal ulcer (1.6%) (Shiokawa Y, et al., 1991). Moreover, the history of peptic ulcer is considered as one of primary risk factors of peptic ulcer occurrence in ‘A Guideline for the Treatment and Prevention of NSAID-associated Ulcers’ (Lanza FL, et al., 1998). The Guideline for the Diagnosis and Treatment of Gastric Ulcer based on EBM (issued in 2007 by a research group for applying and evaluating a guideline for gastric ulcer) also states that the history of ulcer is a risk factor to develop ulcer.

For above reasons a history of gastric and/or duodenal ulcers is included in the criteria as a risk factor to select target subjects for this study.

Rationale for setting the length of treatment period

The treatment period of 52 weeks was also set on the basis of ‘The Size of Population and Treatment Period to Assess Safety at Clinical Study Phase for Drugs Intended for Long-Term Treatment of Non-life-threatening Conditions’ (PMSB Notification No.592 dated 24 May 1995), which reflects ICH E1 guideline.

Rationale for setting the dosage

Based on the results of the overseas clinical studies giving D961H 20 mg and 40 mg once daily (see Table 1, Section 1.2), the dosage approved for prevention of peptic ulcers in the patients receiving NSAID for a long period in the overseas is 20 mg in Europe and 20 to 40 mg once daily in the US.

In Japanese Phase I study, the antisecretory effect was examined in each genotype of CYP2C19 based on the percentage of time with >pH 4 during 24-hour intragastric pH monitoring in the healthy adult males given D961H once daily orally for 5 days. The examined dosage was D961H 10 mg, 20 mg and 40 mg. From the results in 10 mg administration, compared with hetero Extensive Metabolizer (EM) and Poor Metabolizer (PM), the percentage of time with intragastric >pH 4 in homo EM was lower, and its level was similar to the one in placebo. For above reason, it was considered that more definitive antisecretory effect would be needed for prevention of peptic ulcers, and that sufficient antisecretory effect and clinical effect could not be obtained in homo EM with 10 mg. Therefore, 10 mg is not included in this study. In addition, since it is predicted that clinical dose of D961H for treatment of peptic ulcers is 20mg, more than 20 mg as clinical dose for prevention of development of peptic ulcers is not included in this study.

For the above reasons, it is considered appropriate to select D20 as an optimal dose to prevent peptic ulcers in the Japanese patients receiving NSAID for a long period. Therefore, the efficacy and safety of D20 will be investigated in this study.

Rationale for not setting comparator

The safety profile has been well established with results from clinical studies and post-marketing surveillance data in overseas. Results from Phase I study in Japan indicate that the safety profile of Japanese is similar to that of Caucasian. Therefore, it was considered that the safety of D20 in long-term treatment could be sufficiently evaluated as the primary objective in an open-label, single arm study in patients continuously receiving NSAID for a long period.

Rationale for a genetic test

D961H is mainly metabolised by CYP2C19 known as having polymorphic genotype, therefore, it is assumed that the clinical effect of D961H may be influenced by genotype of CYP2C19. In this study the influence of genotype in the patients receiving long-term concomitant treatment with D961H and NSAID will be examined and thus a genetic test of CYP2C19 gene is included.

Rationale for a Hp test

In the meta-analysis for the overseas clinical studies to investigate the relationship of Hp infection and NSAID-associated peptic ulcers, it was concluded that there is a synergistic effect between Hp infection and use of NSAID to increase the ulcers (Huang JQ, et al., 2002). In Japan Hp infection and use of NSAID increase development of upper GI haemorrhage synergistically (Sakamoto C, et al., 2005). Furthermore, 'A Guideline for the Diagnosis and Treatment of Gastric Ulcer based on EBM' suggests the relevance of Hp as it describes that Hp eradication decreases the development of ulcers especially for the patient who are going to use NSAID and the effect for the prevention of NSAID-associated peptic ulcers of Hp eradication is inferior to that of PPI. However, the results of the investigation showed that recurrence rates of gastric ulcers in the three treatment groups of patients with history of Hp negative gastric ulcer, Hp positive gastric ulcer, and Hp eradicated gastric ulcer showed no significant difference between the three groups (Bianchi-Porro G, et al., 1996). It has been reported that the percentage of Hp positive patients with NSAID-associated peptic ulcer is usually lower than those with common peptic ulcer (Mizogami Y, et al., 2005, Chiba T, et al., 2005, Maeda A, et al., 2002). For this, it is considered necessary to conduct a versatile study to investigate the relationship between Hp infection and NSAID-associated peptic ulcers. Based on the above, information on presence or absence of history of Hp infection will be collected in this study as part of demographic data.

Rationale for pepsinogen I/II measurements

It is assumed that numbers of elderly patients are on the long-term treatment with NSAID. Based on the report on the investigation of gastric acid secretory capacity in the adult Japanese population using the index of pH5, gastric pH tends to be increased with age (Morihara M, et al., 2001). For this, patients with hypochlorhydria may be included in the target population aiming at prevention of NSAID-associated peptic ulcers.

On the other hand, considering from the results of the report showing that the incidence of NSAID-associated peptic ulcers increased with age ([Shiokawa Y, et al., 1991](#)) and that the gastric acid secretion inhibitor is also significantly effective for the peptic ulcers induced by the use of NSAID and other various stresses although the acid secretion is not increased in these peptic ulcers ([A Guideline for the Diagnosis and Treatment of Gastric Ulcer based on EBM](#)), it is also considered that NSAID-associated peptic ulcers can be prevented by inhibition of gastric acid secretion.

In this study, the subjects with hypochlorhydria will be specified and the efficacy of D961H in those subjects will be confirmed. In general, progression of gastric mucosa atrophy may cause decreases in gastric acid secretion, therefore, pepsinogen I/II will be measured in order to identify the level of the atrophy in this study.

